### 4.2.3 Notification of Sponsor of Serious Adverse Events

**Within 24 hours of identifying an SAE, regardless of the presumed relationship to the investigational product, the investigator or qualified designee must complete the SAE Report form and fax to MedImmune Product Safety.**

MedImmune contact information:

Product Safety  
MedImmune

[REDACTED]  
Fax: [REDACTED]

MedImmune, as sponsor of the study being conducted under an Investigational New Drug Application (IND), is responsible for reporting certain SAEs as IND safety reports to the FDA, other applicable regulatory authorities, and participating investigators, in accordance with the U.S. Code of Federal Regulations (21 CFR 312.32 and 312.33) ICH Guidelines, and/or local regulatory requirements. MedImmune may be required to report certain SAEs to regulatory authorities within 7 calendar days of being notified about the event; therefore, it is important that investigators submit additional information requested by MedImmune as soon as it becomes available.

Investigators should provide all available information at the time of form completion. Investigators should not wait to collect additional information to fully document the event before notifying MedImmune of an SAE. When additional information becomes available, submit a follow-up SAE report form with the new information. Any follow-up information to an SAE also needs to be provided to MedImmune Product Safety within 24 hours of learning of the new information.

#### **4.2.4 Notification of Institutional Review Board or Independent Ethics Committee of Serious Adverse Events**

The investigator must comply with the applicable regulatory requirements related to the reporting of SAEs to the Institutional Review Board (IRB) or Independent Ethics Committee (IEC). The IRB or IEC must be informed in a timely manner by the principal investigator of serious AEs occurring at their site through Study Day 84. Investigators must also submit safety information provided by MedImmune to the IRB or IEC as detailed in Section 7.2.

#### **4.2.5 Recording of Serious Adverse Events**

Serious adverse events will be recorded on the SAE REPORT FORM using a recognized medical term or diagnosis that accurately reflects the event. SAEs will be assessed by the investigator for severity, relationship to the investigational product, and possible etiologies. See Section 4.2.1 for the definition of SAEs, and Section 4.3 and Section 4.4 regarding guidelines for assessment of severity and relationship, respectively.

For the purposes of study analysis, if the event has not resolved at the end of the study reporting period it will be documented as ongoing. For purposes of regulatory safety monitoring the investigator is required to follow the event to resolution and report to the Sponsor the outcome of the event using the SAE REPORT FORM.

### **4.3 Assessment of Severity**

Assessment of severity is one of the responsibilities of the investigator in the evaluation of AEs and SAEs. The determination of severity should be made by a health care professional who is qualified to review AE information, provide a medical evaluation of AEs, and classify AEs based upon medical judgment and the severity categories of mild, moderate, and severe provided below and in the toxicity table (Appendix 1).

Another consideration to assist investigators in distinguishing between severity levels would include the level of medical intervention required in response to the adverse event. For example, in general, an event of *Mild* severity may include symptomatic over-the-counter treatment managed by the subject. An event of *Moderate* severity may require general symptomatic medical intervention by a health care professional. In contrast, a *Severe* adverse event would generally require more immediate medical evaluation and intervention by a health care professional.

Mild:	Mild level of discomfort and does not interfere with regular activities
Moderate:	Moderate level of discomfort and significantly interferes with regular activities
Severe:	Significant level of discomfort and prevents regular activities>

It is important to distinguish between serious and severe AEs. Severity is a measure of intensity whereas seriousness is defined by the criteria in Section 4.2.1. An AE of severe intensity need not necessarily be considered serious. For example, nausea that persists for several hours may be considered severe nausea, but not an SAE. On the other hand, a stroke that results in only a limited degree of disability may be considered a mild stroke, but would be an SAE.

#### 4.4 Assessment of Relationship

An AE is considered “product-related” for the purposes of regulatory reporting if the investigator, the medical monitor, or the product safety physician assesses the AE as possibly, probably, or definitely related to investigational product. This is not a conclusive determination of causal association between the product and the event.

Whenever the investigator’s assessment is unknown or unclear, the AE is treated as product-related for the purposes of reporting to regulatory authorities. An AE may be deemed to be not related to the product for purposes of regulatory reporting only if the investigator, medical monitor, and product safety physician, if applicable, agree that the AE is not product-related.

The investigator is required to provide an assessment of relationship of AEs and SAEs to the investigational product. A number of factors should be considered in making this assessment including: 1) the temporal relationship of the event to the administration of investigational product; 2) whether an alternative etiology has been identified; and 3) biological plausibility. The following guidelines should be used by investigators to assess the relationship of an AE to investigational product administration.

##### Relationship assessments that indicate an “Unlikely Relationship” to investigational product:

None:	The event is related to an etiology other than the investigational product (the alternative etiology must be documented in the study subject’s medical record).
--------------	---

*Remote:*

The event is unlikely to be related to the investigational product and likely to be related to factors other than investigational product.

Relationship assessments that indicate a “**Likely Relationship**” to investigational product:

*Possible:*

There is an association between the event and the administration of the investigational product and there is a plausible mechanism for the event to be related to investigational product; but there may also be alternative etiology, such as characteristics of the subject’s clinical status or underlying disease.

*Probable:*

There is an association between the event and the administration of investigational product, a plausible mechanism for the event to be related to the investigational product and the event could not be reasonably explained by known characteristics of the subject’s clinical status or an alternative etiology is not apparent.

*Definite:*

There is an association between the event and the administration of investigational product, a plausible mechanism for the event to be related to the investigational product and causes other than the investigational product have been ruled out and/or the event re-appeared on re-exposure to the investigational product.

For AEs that occur prior to the administration of investigational product, an assessment of protocol relatedness must be made. Protocol-related AEs may occur as a result of procedures required during the screening process (eg, blood collection, washout of an existing medication) prior to the initial administration of investigational product. For AEs that occur before administration of investigational product, only those that are assessed by the investigator as protocol-related should be reported to the sponsor. The following guidelines should be used by investigators to assess the relationship of an AE to a protocol-required procedure:

*Protocol related:*

The event occurred due to a procedure/intervention that was described in the protocol for which there is no alternative etiology present in the subject’s medical record.

Not protocol related: The event is related to an etiology other than the study procedure (the alternative etiology must be documented in the study subject's medical record).

#### **4.5 Other Events Requiring Immediate Reporting**

The following events must be reported *within 24 hours* by fax to MedImmune Product Safety using the fax notification form:

- 1) Any withdrawal of consent during the study
- 2) Pregnancy or intent to become pregnant\*
- 3) Anaphylactic (see Section 4.7) or infusion reaction (see Section 4.9)

\* Subjects who become pregnant from Study Day 0 through Study Day 84 will be followed for the duration of the study. A pregnancy should be followed for outcome, any premature terminations reported, and the health status of the mother and child including date of delivery and the child's gender and weight should be reported to MedImmune Product Safety after delivery.

#### **4.6 Safety Management During the Study**

The MedImmune medical monitor has primary responsibility for the ongoing medical review of safety data throughout the study. This includes immediate review of SAEs and timely review of other AEs reported through Study Day 84. The MedImmune Product Safety Specialist has responsibility for the day-to-day safety monitoring of the study, including the receipt, review, investigation, and follow-up of SAEs reported by the clinical study sites.

The Safety Monitoring Committee (SMC) will independently review cumulative safety surveillance data on a regular basis throughout the study and make recommendations regarding further conduct of the study. The SMC will also review safety data at other time points in response to AEs felt to be medically significant by the medical monitor. The SMC is composed of at least 2 MedImmune physicians who are not directly involved in the day to day operations of the study, and at least 2 physicians who are not employees of MedImmune. The SMC will review blinded safety surveillance data reported to MedImmune, but may request to be unblinded if necessary to make safety assessments and study recommendations.

#### **4.7 Interruption or Discontinuation of Study Dosing in Individual Subjects**

An individual subject will not receive any further investigational product if any of the following occur in the subject in question during the infusion:

- 1) Withdrawal of consent
- 2) Event which in the opinion of the investigator contraindicates further administration of investigational product such as illnesses or complications
- 3) Anaphylactic reaction to MEDI-563 (defined in [Appendix 2](#))

Subjects who are permanently discontinued from investigational product will be followed for the full study period (through Study Day 168), including the collection of any protocol-specified blood specimens, unless consent is withdrawn.

#### **4.8 Interruption or Discontinuation of Study Dosing and Randomization**

If any of the following occur, no further administration of investigational product will take place and no further subjects will be randomized into the study:

- 1) Death in any subject in which the cause of death is assessed as possibly, probably, or definitely related to investigational product
- 2) Any anaphylactic event (defined in [Appendix 2](#)) or 2 serious allergic events judged related to investigational product.
- 3) Two infusion reactions judged related to the investigational product.
- 4) The occurrence of immune complex disease.
- 5) Events that, in the opinion of the medical monitor and the Safety Monitoring Committee (SMC), contraindicate further dosing of additional subjects.

If one of the above-listed events occurs, a prompt cumulative review of safety data and the circumstances of the event in question will be conducted by the medical monitor and the SMC to determine whether dosing and study entry/randomization should be resumed, whether the protocol will be modified, or whether the study will be discontinued permanently. Review and approval by the SMC are required for resumption of the study in the event the study is interrupted because of one of the above-listed events.

#### **4.9 Monitoring of Dose Administration**

Vital signs will be monitored before and after investigational product administration.

As with any MAb, allergic reactions and infusion reactions to dose administration are possible. Therefore, appropriate drugs and medical equipment to treat acute anaphylactic reactions must be immediately available, and study personnel must be able to recognize and treat infusion reactions and allergic reactions such as anaphylaxis.

Infusion reactions usually occur within the first 24 hours after infusion and are characterized by a complex of symptoms that may include flu-like illness, fever, chills/rigors, nausea, urticaria, headache, bronchospasm, angioedema, hypotension, hypoxia, pulmonary infiltrates, acute respiratory distress syndrome, myocardial infarction, ventricular fibrillation, and cardiogenic shock.

Anaphylaxis is defined as a serious allergic reaction that is rapid in onset and may cause death ([Sampson et al, 2006](#)). See [Appendix 2](#) for the clinical criteria for defining anaphylaxis.

If an anaphylactic or an infusion reaction occurs, the infusion will be stopped and a serum sample will be drawn for mast cell tryptase, histamine, TNF-alpha, and IL-1.

## **5 Statistical Considerations**

### **5.1 General Considerations**

All data will be provided in data listings sorted by treatment groups (MEDI-563 0.3 mg/kg, MEDI-563 1.0 mg/kg, or placebo), and visit number. Summary data will be presented in tabular format by treatment groups. Categorical data will be summarized by the number and percentage of subjects in each category. Continuous variables will be summarized by descriptive statistics including N, mean, standard deviation, median, and range. Statistical hypothesis testing, if appropriate, will be performed for the primary endpoint with a 2-sided test.

A comprehensive statistical analysis plan will be developed and approved prior to the database lock.

### **5.2 Sample Size and Power Calculations**

#### **5.2.1 Planned Sample Size**

Sample size calculations have been performed for the primary endpoint of proportion of subjects with asthma exacerbations at Week 12 to allow for hypothesis testing. Sample size calculations are based on Fisher's exact test with  $\alpha = 0.05$  (2-sided) for testing the difference between the combined MED-563 treatment groups ( $n=72$ , 0.3 mg/kg and 1.0 mg/kg) and the combined placebo group ( $n=36$ ). Assumptions include: (1) The proportion of placebo subjects with asthma exacerbations at Week 12 is 60% and (2) There will be  $\geq 50\%$

reduction in the proportion of subjects with asthma exacerbations at Week 12 in the combined MEDI-563 (0.3 and 1.0 mg/kg) treatment groups. The sample size may be re-estimated using the proportion of subjects with asthma exacerbations (relapsed or de novo) up to the first interim analysis to preserve the power around 80% if the proportion of subjects with asthma exacerbations is different from the assumptions listed above.

There will be no adjustment on Type 1 error rate for sample size re-estimation in this study. However, the true overall type I error rate will be greater than 0.05 if the multiplicity adjustment is taken into account in the calculation. With 108 evaluable subjects, the statistical power to detect statistically significant differences in the proportion of subjects with asthma exacerbations at Week 12 in the combined MEDI-563 treatment groups and the placebo group will be 80% based on the above assumptions. Power calculations were performed using nQuery Advisor software program Version 6.01.

Table 5.2.1-1 and [Table 5.2.1-2](#) present the probability of observing at least one infrequently occurring event when assuming a range of potential observed event rates and exact binomial 95% confidence intervals to assess the precision of estimates of the event rate for each individual treatment group (n=36) and combined MEDI-563 treatment group (n=72).

**Table 5.2.1-1 Expected Number of Events and Probabilities of Observing at Least 1 or 2 Events Given the True Event Rates**

N	True Event Rate (%)	Number of Events Expected	Probability of Observing at least 1 Event (%)	Probability of Observing at least 2 Events (%)
36	0.2	0	7.0	0.2
36	0.4	0	13.4	0.9
36	0.5	0	16.5	1.4
36	1.0	0	30.4	5.0
36	1.5	1	42.0	10.1
36	2.0	1	51.7	16.2
36	2.5	1	59.8	22.7
72	0.2	0	13.4	0.9
72	0.4	0	25.1	3.4
72	0.5	0	30.3	5.1
72	1.0	1	51.5	16.2
72	1.5	1	66.3	29.4

**Table 5.2.1-1 Expected Number of Events and Probabilities of Observing at Least 1 or 2 Events Given the True Event Rates**

N	True Event Rate (%)	Number of Events Expected	Probability of Observing at least 1 Event (%)	Probability of Observing at least 2 Events (%)
72	2.0	1	76.7	42.3
72	2.5	2	83.8	54.0

**Table 5.2.1-2 Estimated Event Rates and 95% Exact Binomial Confidence Intervals Given the Number of Events Observed**

N	Number of Events Observed	Estimated Event Rate (%)	95% Confidence Interval
36	0	0.0	(0.0%; 9.7%)
36	1	2.8	(0.1%; 14.5%)
36	2	5.6	(0.7%; 18.7%)
36	3	8.3	(1.8%; 22.5%)
72	0	0.0	(0.0%; 5.0%)
72	1	1.4	(0.0%; 7.5%)
72	2	2.8	(0.3%; 9.7%)
72	3	4.2	(0.9%; 11.7%)

## 5.2.2 Re-estimation of Sample Size

The sample size may be re-estimated based on the results of the first interim analysis as listed below. Examples of sample size estimates for the different assumptions are listed in Table 5.2.2-1.

- Sample size will be re-estimated if the proportion of subjects with asthma exacerbations (relapsed or de novo) at Week 12 is greater than or equal to 45% but less than 55%. Assumptions to re-estimate the sample size will be alpha = 0.05 (2-sided), current proportion of placebo subjects with asthma exacerbations, and a 50% reduction in the combined MEDI-563 groups.
- The sample size will not be re-estimated if the proportion of placebo subjects with asthma exacerbations (relapsed or de novo) through Week 12 is less than 45%.

- The study may be terminated if proportions of subjects with asthma exacerbations in the combined MEDI-563 groups at the interim analysis is approximately the same or lower than that in the placebo group.

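### The sample-size re-estimation trigger omits the word placebo, and even with it restored the rule does not hold power near 80% when the placebo rate is low

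*Protocol*

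**What the plan says.** Section 5.2.1 sizes the trial at 36 placebo and 72 MEDI-563 subjects. "Sample size calculations are based on Fisher's exact test with" a two-sided alpha of 0.05, and the planning assumption is: "The proportion of placebo subjects with asthma exacerbations at Week 12 is 60"%, with at least a 50% reduction on MEDI-563. The stated power is 80%. The section gives the purpose of re-estimation as "to preserve the power around 80% if the proportion of subjects with asthma exacerbations is different from the assumptions listed above".

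Section 5.2.2 gives the rule. The first bullet reads: "Sample size will be re-estimated if the proportion of subjects with asthma exacerbations (relapsed or de novo) at Week 12" is at least 45% but less than 55%. Its second sentence sets the inputs for the new calculation: "alpha = 0.05 (2-sided), current proportion of placebo subjects with asthma exacerbations". The effect assumed there is "a 50% reduction in the combined MEDI-563 groups". For values under 45%, the second bullet applies: "The sample size will not be re-estimated if the proportion of placebo subjects with asthma exacerbations (relapsed or de novo) through Week 12". Table 5.2.2-1 is indexed by the placebo proportion: 0.54, 0.50 and 0.45 give totals of 129, 147 and 171. The Study Abstract repeats the bullets. Section 5.6 places the first interim analysis after at least 44 treated subjects have completed Day 84.

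**The concern.** The trigger names no arm, so on its face it refers to all subjects at the interim. Everything around it refers to placebo. In a trial with twice as many active as placebo subjects and an assumed halving of the event rate, the two proportions differ by a third, so the same interim data can lead to different decisions.

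Two illustrative interim results show this:

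- 7 of 15 placebo and 7 of 29 active subjects with an exacerbation. The placebo proportion is 46.7%, inside the band. The all-subject proportion is 14/44 = 31.8%, outside it. The trial is enlarged on one reading and not on the other.
- 11 of 15 and 10 of 29. The placebo proportion is 73.3%, outside the band. The all-subject proportion is 21/44 = 47.7%, inside it. The literal rule would re-estimate a trial that is already amply sized.

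The second issue is separate from the wording. The protocol tells its readers that re-estimation protects power if the event rate is off target, but the rule withholds re-estimation at the placebo rates where the loss is largest.

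**Working it through.** **Inputs.** Two-sided Fisher's exact test at 0.05, 36 placebo and 72 active, 60% versus 30% (Section 5.2.1); 2:1 allocation (Section 2.3); band of 45% to under 55%, 50% reduction and Table 5.2.2-1 (Section 5.2.2); interim at 44 subjects (Section 5.6). Assumption: exactly 44 subjects, and since 44/3 = 14.7, 15 on placebo and 29 on active.

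**Step 1: the protocol's own figures.** Exact power, summing both binomial distributions over every table that Fisher's test rejects, is 81.1% at 36/72. The continuity-corrected formula gives 36 placebo subjects (108 in total) for the design, and 43, 49 and 57 placebo subjects (129, 147 and 171 in total) for the three table rows. All the stated sizes reproduce.

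**Step 2: converting the trigger.** With placebo proportion p and active proportion p/2, the all-subject proportion is p/3 + (2/3)(p/2) = 2p/3.

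- Design: (36 × 0.60 + 72 × 0.30)/108 = 40%, already below the band.
- Table rows 0.54, 0.50 and 0.45: 36%, 33% and 30%, all below the band.
- Band limits converted back: 0.45 × 1.5 = 67.5% and 0.55 × 1.5 = 82.5% placebo. Exact power with 108 subjects there is 89.9% and 99.1%. The continuity-corrected totals needed for 80% power are 90 and 60, fewer than are already planned.

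**Step 3: how often the literal trigger fires.** With 44 subjects the band contains 20 to 24 events in total. Adding Binomial(15, p) and Binomial(29, p/2):

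| True placebo rate | Probability literal trigger fires |
|---|---|
| 60% (design) | 26% |
| 54% | 12% |
| 50% | 6% |
| 45% | 2% |

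It fires most often in the one row where no increase is needed.

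**Step 4: placebo reading, power where 108 subjects are kept.** Exact Fisher power at 36/72 with a 50% reduction:

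| True placebo rate | Power at 108 |
|---|---|
| just under 45% | 62% |
| 40% | 55% |
| 35% | 47% |

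The two-sided p-value here sums the point probabilities no larger than the observed one. With 0.025 in each tail, the three figures are 58%, 51% and 43%.

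**Step 5: placebo reading, power over the whole rule.** With 15 placebo subjects only 7/15 (46.7%) and 8/15 (53.3%) fall in the band. Interpolating Table 5.2.2-1 gives 54 and 44 placebo subjects, or 162 and 132 in total; any other count keeps 108. Power is the sum over x = 0 to 15 of P(x placebo events at the interim) × P(final Fisher test rejects, given x and the resulting size). The stopping provision in the third bullet is ignored; using it could only lower these figures.

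| True placebo rate | Interim result in band | Observed rate below 45% | Power over the rule |
|---|---|---|---|
| 50% | 39% | 30% | 74% |
| 45% | 37% | 45% | 67% |
| 40% | 30% | 61% | 58% |

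At a true rate of 50%, where the table promises 81%, the interim is too small to find the band reliably.

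**The case against.** The best defence is that the intended meaning can be recovered. The trigger's own second sentence, the second bullet's matching 45% cut-off and the table all point to placebo, so this is one omitted word with one coherent reading. That stands, and it is why the repair is small. It does not make the sentence safe: it is the operative decision rule, it appears twice, and its literal meaning is a different rule.

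It can also be said that keeping 108 subjects below 45% is an explicit choice, possibly for feasibility, under a clause that only says the size may be re-estimated. That also stands as far as the choice goes. What it does not support is the stated purpose in Section 5.2.1, since no reason and no resulting power are given.

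A reader might go further on several points that the documents do not support:

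- *That the literal trigger never fires for the table's cases.* The expected all-subject proportions lie below the band, but with 44 subjects chance still puts the observed value inside it 2% to 12% of the time.
- *That no re-estimation occurs at 45%.* The band includes 45%, and the table has a 0.450 row; only lower rates are excluded.
- *That the absence of a rule for 55% to 60% loses power.* At a fixed 108, power there is 75% to 81%. Over the whole rule it is about 81% to 86%, because some interim results fall in the band by chance and enlarge the trial.
- *That the type I error sentence is wrong.* The protocol says "the true overall type I error rate will be greater than 0.05 if the multiplicity adjustment is taken into account in the calculation". The pooled primary test is done once, and re-estimation alone need not push its size above 0.05. But the sentence concerns overall error and multiplicity, and Section 5.4 allows per-dose Fisher tests at Week 12, which it can be read to cover.
- *That a blinded all-subject trigger of 30% to under 40% should be used instead.* That is a design preference, not a correction. Its upper limit is the planned value, and it would trigger about 39% of the time with the design assumptions true.

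**Conclusion.** The point holds in two parts. First, the trigger as written refers to the wrong proportion. The literal band corresponds to placebo rates of 67.5% to 82.5%, where 108 subjects give 90% to 99% power, and it would be met only 12%, 6% and 2% of the time at the placebo rates of 54%, 50% and 45% that the table sizes. Second, even on the placebo reading the aim of holding power near 80% is not met. Power is at most about 62% where 108 subjects are kept below 45%, and about 74%, 67% and 58% over the whole rule at true rates of 50%, 45% and 40%.

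The conversion rests on 2:1 allocation and the protocol's assumed 50% reduction. The firing probabilities and the whole-rule powers also assume 15 placebo subjects (and, for the former, 29 active) at the interim, and the whole-rule powers assume linear interpolation of the table. The sample sizes in the protocol are correct; the fault lies in the trigger wording and the power claim.

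**What to change.** 1. In the first bullet, insert *placebo* before *subjects* in the trigger, both in Section 5.2.2 and in the Study Abstract.
2. In Section 5.2.1 and the matching sentence of the Study Abstract, replace the statement that power is kept near 80% with the computed power of the rule: about 74%, 67% and 58% at true placebo rates of 50%, 45% and 40%, with the interim assumption stated. Say plainly that power is not preserved below 45%, where 108 subjects give at most about 62% (55% at 40%, 47% at 35%).

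The cost is wording and a short calculation. The design, the table and the analysis stay as they are. The downside is that the stated power becomes less favourable at low placebo rates.

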## 1.5 Rationale for Study

The present study will evaluate the effect of two IV dose regimens of MEDI-563 (0.3 and 1.0 mg/kg) on the asthma exacerbation rate (relapse and de novo) in adult subjects who required an urgent healthcare visit for treatment of an acute asthma exacerbation. Given that acute asthma in some subjects may have an eosinophilic component, administration of MEDI-563 upon discharge from an urgent healthcare setting should reduce asthma exacerbations due to better asthma control. In addition, administration of a single IV infusion of MEDI-563 may improve asthma control, particularly in those subjects who are not compliant with a continuous intake of corticosteroids to avert acute exacerbations ([Burney et al, 2008](#)).

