### **3.6.10 Disease Evaluations**

#### **3.6.10.1 Asthma Exacerbations**

Asthma exacerbation data will be collected through Study Day 168. For the purpose of this study, an asthma exacerbation (relapse or de novo) is defined as either 1) an increase of asthma symptoms (cough, wheeze, chest tightness, and/or shortness of breath) that does not resolve within 2 hours after the use of rescue albuterol or corticosteroids and requires an unscheduled medical visit or 2) during a scheduled study visit, the subject has acute worsening of asthma symptoms and a reduction of  $\geq 20\%$  in PEF or FEV1, which in the opinion of the investigator requires treatment with systemic corticosteroids.

An exacerbation event will be considered resolved if the subject's acute asthma symptoms diminish or PEF or FEV1 return to  $> 80\%$  of baseline for  $> 7$  days after completion of oral steroid burst therapy.

The following information will be collected for each asthma exacerbation:

- Date of onset
- Date of visit to healthcare provider or ED
- Treatment
- Resolution date

In this study, 2 aspects of asthma exacerbations will be collected: (1) number of subjects with at least one exacerbation during the study, and (2) number of exacerbations per subject in each treatment group.

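### The interim termination rule runs the wrong way: as written, the study may be stopped when MEDI-563 subjects have fewer exacerbations than placebo

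*Protocol*

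**What the plan says.** Section 5.2.2 lists three decisions that may follow the first interim analysis. The first two concern re-estimating the sample size. The third allows the study to be terminated if the proportion of subjects with exacerbations "in the combined MEDI-563 groups at the interim analysis is approximately the same or lower than that in the placebo group". The Study Abstract repeats it in the same words under its own re-estimation heading.

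Elsewhere the protocol fixes the direction of benefit:

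- Section 3.6.10.1 defines an exacerbation as a worsening. Its first limb is "an increase of asthma symptoms (cough, wheeze, chest tightness, and/or shortness of breath) that does not resolve within 2 hours" after rescue treatment and needs an unscheduled medical visit.
- Section 1.5 says that giving MEDI-563 "should reduce asthma exacerbations due to better asthma control".
- Section 5.2.1 assumes a 60% placebo proportion and a reduction of at least half on MEDI-563. Section 5.2.2 re-estimates with "a 50% reduction in the combined MEDI-563 groups", and every row of Table 5.2.2-1 sets the MEDI-563 proportion at half the placebo one.

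Section 5.6 says that the first interim takes place after at least 44 treated subjects have completed Day 84 and serves to re-estimate the sample size. The primary test belongs to the second interim.

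**The concern.** A lower MEDI-563 proportion is what the trial is designed to find, yet it is listed as a ground for ending the trial. A higher MEDI-563 proportion, the ordinary trigger for a futility stop, is not listed anywhere in the rule.

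Followed literally, a drug that works meets the termination condition at the first interim and a drug that makes matters worse usually does not. Unblinded interim results go to a small group of senior sponsor managers outside the study team (Sections 3.3 and 5.6). A written rule exists so that their decision does not rest on interpretation after seeing the data. With this wording, a futility stop for a worse result on MEDI-563 would have no support in the text, while a stop on a favourable result would.

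**Working it through.** **Inputs.** Placebo proportion 60%, MEDI-563 proportion 30%, Fisher's exact test, two-sided alpha 0.05, 36 placebo and 72 MEDI-563 subjects (Section 5.2.1); 2:1 allocation (Section 2.3); first interim at 44 or more subjects (Section 5.6). Assumptions of this check: the 44 split as 15 placebo and 29 MEDI-563; near-equality, which the protocol does not define, is a margin *m* of 0, 5 or 10 percentage points; the harmful scenarios (75% or 80% on MEDI-563) are illustrative.

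**Step 1: the plan's own figure.** "Sample size calculations are based on Fisher's exact test", and the power "will be 80% based on the above assumptions". Summing the two binomial distributions over all outcomes that Fisher's test rejects, for 36 at 0.60 against 72 at 0.30, gives 81.1%. The continuity-corrected sample size formula with 2:1 allocation gives 36, 43, 49 and 57 placebo subjects for placebo proportions of 0.60, 0.54, 0.50 and 0.45. These match the base design and all three rows of Table 5.2.2-1. The planning figures are reproduced, and they all have MEDI-563 lower than placebo.

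**Step 2: how often the condition is met.** Let X ~ Bin(15, p_P) be placebo events and Y ~ Bin(29, p_M) be MEDI-563 events. Then

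- as written: P(Y/29 − X/15 ≤ *m*)
- reversed: P(Y/29 − X/15 ≥ −*m*)

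Exact enumeration, for *m* = 0 / 5 / 10 points:

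| True proportions (placebo vs MEDI-563) | As written | Reversed |
|---|---|---|
| 60% vs 30% (design) | 97.2 / 98.9 / 99.5% | 2.8 / 4.5 / 10.2% |
| 60% vs 60% (no effect) | 51.2 / 59.9 / 74.9% | 48.8 / 64.2 / 73.2% |
| 60% vs 75% (harm) | 17.1 / 23.5 / 39.2% | 82.9 / 92.0 / 95.0% |
| 60% vs 80% (harm) | 9.5 / 14.1 / 27.1% | 90.5 / 96.3 / 97.9% |

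Hand check of the first cell: the expected difference is −0.30, with standard error √(0.6×0.4/15 + 0.3×0.7/29) = √(0.01600 + 0.00724) = 0.152. Then 0.30/0.152 = 1.97, and Φ(1.97) ≈ 0.976, close to the exact 0.972. With a 14/30 split, the as-written column at *m* = 0 is 96.9%, 52.6% and 16.9% for the first three rows.

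**Step 3: effect on the primary analysis at 60% vs 30%.** Each interim outcome was carried forward to the final Fisher test. The sample size was re-estimated when the observed placebo proportion was at least 45% and below 55% (7/15 = 46.7% or 8/15 = 53.3%), using the formula from Step 1; otherwise it stayed at 36 and 72. Reading the 45–55% band as the placebo proportion is an assumption. Probability of a significant result:

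| Handling of the rule | Power |
|---|---|
| No stop | 86.1% |
| As written, *m* = 0, always followed | 0.8% |
| Reversed, *m* = 0 | 85.3% |
| Reversed, *m* = 5 points | 84.5% |
| Reversed, *m* = 10 points | 80.9% |

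**The case against.** Four points can be made on the other side.

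- **The rule is permissive.** It says that the study may be terminated, and managers who know the hypothesis would probably recognise a slip. This stands as a limit on the size: 0.8% is what literal, unfailing use would give, not the expected outcome. It does not make the text usable, because the decision would then rest on guessing the intent after unblinding.
- **Safety oversight exists.** The Safety Monitoring Committee (Section 4.6) and the halting rules (Section 4.8) can stop dosing and randomization. This also stands: the trial is not without protection, and the criticism applies to this rule only. Those provisions act on safety events and judgement, however, and contain no comparison of exacerbation proportions between arms.
- **It might be an early-success rule.** This fails. Near-equality and a lower proportion are joined in one condition, and nobody stops for success when the arms are alike. The protocol gives no efficacy boundary, and Section 5.6 places the primary test at the second interim.
- **A zero-margin threshold drops the allowance for near-equality.** This is fair as a matter of choice. The protocol gives no margin, so some number has to be chosen, and the power cost depends on it: 0.8 points at zero (86.1 − 85.3), 1.6 at 5 points (86.1 − 84.5) and 5.2 at 10 points (86.1 − 80.9).

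**Conclusion.** The concern holds. The rule contradicts the protocol's endpoint definition, rationale and power assumption, in both places where it appears and in current text. It is most likely to be met when the drug works (97.2% at the design rates) and least likely when it harms (9.5% at 60% versus 80%), the opposite of what a futility rule should do. These figures rest on a 15/29 split at the interim and a zero margin. The 14/30 split changes them little, and wider margins raise the chance that the written rule is met when the drug works. It must be corrected before the first interim analysis.

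**What to change.** In Section 5.2.2 and in the Study Abstract, reverse the direction so that termination may be considered when the MEDI-563 proportion is the same as or higher than placebo, and replace the undefined near-equality with a number. Suggested criterion: at the first interim, the observed proportion with at least one exacerbation in the combined MEDI-563 groups is greater than or equal to the observed placebo proportion, stated as non-binding. If the sponsor wants an allowance for near-equality, give the margin in percentage points and accept the power cost shown above.

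With the zero margin, the rule would be met 2.8% of the time at the design rates and 48.8% of the time with no effect at 60%, for a loss of 0.8 points of power. A stop for futility cannot increase the chance of a false positive, so the change needs no alpha adjustment of its own. The cost is a short protocol amendment in two places, with no added subjects or procedures.
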